9.5.1.5.1 ADVERSE EVENTS AND EVENTS ASSOCIATED WITH SPECIAL SITUATIONS

An AE is any untoward medical occurrence in a patient or clinical investigation subject administered an investigational product. An AE does not necessarily have a causal

relationship with the medicinal product. For this study, the study drug is Belviq XR (lorcaserin hydrochloride).

The criteria for identifying AEs in this study are:

- Any unfavorable and unintended sign (including an abnormal laboratory finding), symptom, or disease temporally associated with the use of an investigational product, whether or not considered related to the investigational product (Note: Every sign or symptom should not be listed as a separate AE if the applicable disease [diagnosis] is being reported as an AE)
- Any new disease or exacerbation of an existing disease
- Any deterioration in non-protocol-required measurements of a laboratory value or other clinical test (eg, ECG, x-ray) that results in symptoms, a change in treatment, or discontinuation of study drug
- Recurrence of an intermittent medical condition (eg, headache) not present at pretreatment (baseline)
- An abnormal laboratory test result should be considered an AE if the identified laboratory abnormality leads to any type of intervention, withdrawal of study drug, or withholding of study drug, whether prescribed in the protocol or not.

All AEs observed during the study will be reported on the Adverse Event CRF. All AEs, regardless of relationship to study drug or procedure, should be collected beginning from the time the subject signs the study ICF through the last visit in the Treatment Phase. Subjects who fail screening primarily due to AE(s) must have the AE(s) leading to screen failure reported on the Screening Disposition CRF. SAEs will be collected for 28 days after the last dose.

Abnormal laboratory values should not be listed as separate AEs if they are considered to be part of the clinical syndrome that is being reported as an AE. It is the responsibility of the investigator to review all laboratory findings in all subjects and determine if they constitute an AE. Medical and scientific judgment should be exercised in deciding whether an isolated laboratory abnormality should be classified as an AE. Any laboratory abnormality considered to constitute an AE should be reported on the Adverse Event CRF.

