9.5.2 Schedule of Procedures/Assessments

9.5.2.1 Schedule of Procedures/Assessments

Table 2 presents the Schedule of Procedures/Assessments for the study.

Phase:	Prerandomization ^a	Randomization													
Period:	Screening	Treatment ^b											Follow-Up		
Visit Number:	1	2 ^a	3	4	5	6	7	8	9	10	11 (EOT)	EOS	US ^c	ED	
Day:	-30 to -1	1													
Weeks:		0	1	5	8	12	20	28	36	44	52	56			
Procedure															
Informed Consent	X														
Demography	X														
Medical History	X														
Prior/concomitant medication assessments	X	X	X	X	X	X	X	X	X	X	X	X	X	X	
AE monitoring	X	X	X	X	X	X	X	X	X	X	X	X	X	X	
Inclusion/exclusion criteria	X	X													
Physical Examination ^d	X	X	X			X		X			X	X	X	X	
Vital signs	X	X	X	X	X	X	X	X	X	X	X	X	X	X	
Height	X	X	X	X	X	X	X	X	X	X	X	X	X	X	
Weight	X	X	X	X	X	X	X	X	X	X	X	X	X	X	
Waist circumference	X	X		X		X		X	X		X	X	X	X	
CDC growth chart	X	X		X		X		X	X		X	X	X	X	
Tanner Staging		X						X			X	X	X	X	
Routine clinical laboratory tests	X	X	X	X		X		X			X	X		X	
Urinalysis	X	X	X	X		X		X			X	X		X	
Urine drug and cotinine test	X														
Fasting plasma glucose, insulin, and HbA1c sampling	X	X				X		X			X			X	
T4 and TSH	X	X						X			X			X	
Testosterone, Estradiol ^e		X						X			X				

Table 2 Schedule of Procedures/Assessments in Study APD356-A001-403 (revised per Amendments 01, 02, 03, and 04)															
Phase:	Prerandomization^a	Randomization													
Period:	Screening	Treatment^b											Follow-Up		
Visit Number:	1	2 ^a	3	4	5	6	7	8	9	10	11 (EOT)	EOS	US ^c	ED	
Day:	-30 to -1	1													
Weeks:		0	1	5	8	12	20	28	36	44	52	56			
Procedure															
Pregnancy test (urine)	X	X	X	X	X	X	X	X	X	X	X	X		X	
Fasting prolactin	X	X				X		X			X			X	
OC, PICP, and Hydroxy-proline		X						X			X			X	
Fasting lipid panel		X						X			X			X	
Urine NTX		X						X			X			X	
PK/PD blood sampling						X ^f		X ^f	X ^f		X ^{f,g}		X ^h	X ^g	
AM serum cortisol		X									X			X	
ECG		X						X			X	X			
Echocardiograph	X ⁱ							X			X				
DEXA ^j		X									X				
Randomization		X													
IxRS	X	X		X	X	X	X	X	X	X	X				
Study drug dispensing		X		X	X	X	X	X	X	X			X		
Collect study medication				X	X	X	X	X	X	X	X	X	X	X	
Drug accounting and compliance			X	X	X	X	X	X	X	X	X		X	X	
Hand x-ray for bone age		X									X			X	
C-SSRS	X		X	X	X	X	X	X	X	X	X	X	X	X	
Leiter-3		X		X				X			X	X		X	
PHQ-9		X	X	X	X	X	X	X	X	X	X	X	X	X	

Phase:	Prerandomization ^a	Randomization													
Period:	Screening	Treatment ^b											Follow-Up		

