9.5.4.1 Reporting of Serious Adverse Events

All SAEs, regardless of their relationship to study treatment, must be reported on a completed SAE form by email or fax as soon as possible but no later than 1 business day from the date the investigator becomes aware of the event.

SAEs, regardless of causality assessment, must be collected through the through the last visit and for 28 days after the subject's last dose. All SAEs must be followed to resolution or, if resolution is unlikely, to stabilization. Any SAE judged by the investigator to be related to the study treatment or any protocol-required procedure should be reported to the sponsor regardless of the length of time that has passed since study completion.

The detailed contact information for reporting of SAEs is provided in the Investigator Study File.

For urgent safety issues, please ensure all appropriate medical care is administered to the subject and contact the appropriate study team member listed in the Investigator Study File.

It is very important that the SAE report form be filled out as completely as possible at the time of the initial report. This includes the investigator's assessment of causality.

Any follow-up information received on SAEs should be forwarded within 1 business day of its receipt. If the follow-up information changes the investigator's assessment of causality, this should also be noted on the follow-up SAE form.

Preliminary SAE reports should be followed as soon as possible by detailed descriptions including copies of hospital case reports, autopsy reports, and other documents requested by the sponsor.

The investigator must notify his/her IRB/IEC of the occurrence of the SAE, in writing, if required by their institution. A copy of this communication must be forwarded to the sponsor to be filed in the sponsor's Trial Master File.

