9.7.1.8.2 ADVERSE EVENTS

The AE verbatim descriptions (investigator terms from the CRF) will be classified into standardized medical terminology using the Medical Dictionary for Regulatory Activities (MedDRA). Adverse events will be coded to the MedDRA (Version 18.0 or higher) lower level term closest to the verbatim term. The linked MedDRA PT and primary system organ class (SOC) are also captured in the database.

A treatment-emergent AE (TEAE) is defined as an AE that emerges during treatment (up to 28 days after the last dose of study drug), having been absent at pretreatment (baseline) or

- Reemerges during treatment (up to 28 days after the last dose of study drug), having been present at pretreatment (baseline) but stopped before treatment, or
- Worsens in severity during treatment relative to the pretreatment state, when the AE is continuous.

Only those AEs that were treatment emergent will be included in summary tables. All AEs, treatment emergent or otherwise, will be presented in subject data listings.

The TEAEs will be summarized by treatment group. The following summaries will be reported for TEAES:

- Incidence of TEAEs in descending order of frequency
- Incidence of TEAEs by SOC and PT
- Incidence of treatment-related TEAEs by SOC and PT
- Incidence of TEAEs by SOC, PT and maximum severity (mild, moderate, or severe)
- Incidence of treatment-related TEAEs by SOC, PT, and maximum severity (mild, moderate, or severe)
- Incidence of TEAEs by SOC, PT, and relationship to study drug (Yes [related] or No [not related])

A subject will be counted only once within a SOC or PT, if the subject experienced more than 1 TEAE within a specified SOC and PT.

The following summaries will also be presented for the treatment-emergent SAEs.

- Incidence of TEAEs leading to death
- Incidence of treatment-emergent SAE by SOC and PT
- Incidence of treatment-related treatment-emergent SAE by SOC and PT

In addition, subjects with TEAEs leading to discontinuation from study drug and AEs of special interest as described in [Section 9.5.4.3.2](#) will be summarized by MedDRA SOC and PT for each treatment group.

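### The protocol gives conflicting end points for collecting non-serious adverse events: the collection rule appears to stop at Week 52, while Table 2 and the treatment-emergent definition run about four weeks longer

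*Protocol*

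**What the plan says.** Four parts of the protocol (version 10.0) bear on when AE collection ends.

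- **Section 9.5.1.5.1, collection rule.** It first states "All AEs observed during the study will be reported on the Adverse Event CRF". The next sentence sets the dates: from signed consent "through the last visit in the Treatment Phase". The paragraph closes with "SAEs will be collected for 28 days after the last dose".
- **Section 9.7.1.8.2, analysis definition.** A treatment-emergent AE (TEAE) is one that "emerges during treatment (up to 28 days after the last dose of study drug), having been absent at pretreatment (baseline"). The definition is not limited to serious events. The section adds: "Only those AEs that were treatment emergent will be included in summary tables".
- **Table 2 (Section 9.5.2.1).** The row "AE monitoring" is marked at every visit, including EOS at Week 56.
- **Section 9.5.4.1, SAE reporting.** SAEs "must be collected through the through the last visit and for 28 days after" the subject's last dose.

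Section 9.1 names two phases, Prerandomization and Randomization. The Randomization Phase contains a Treatment Period of up to 52 weeks and a Follow-Up Period from the End of Treatment (EOT) visit to EOS. No Treatment Phase is defined.

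**The concern.** The collection rule tells sites which events to record, and the TEAE definition tells the analyst which recorded events to count. Here the counting window is longer than the most natural reading of the recording window. For a subject who takes drug to Week 52, the four weeks after EOT lie inside the TEAE definition but outside the dates that Section 9.5.1.5.1 sets for non-serious events.

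Safety is reported descriptively by treatment group without hypothesis tests (Section 9.7.1.8), so the TEAE tables are the AE result. If some sites follow Section 9.5.1.5.1 and others follow Table 2, those tables would mix two ascertainment periods with no way to tell them apart. This is an instruction to sites, so a later analysis plan cannot repair it.

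**Working it through.** There is no stated figure to reproduce. The check compares three windows.

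**Inputs**
- EOT at Week 52 and EOS at Week 56 (Section 9.1, Table 2)
- Visit window of ±7 days (Table 2, footnote b)
- TEAE tail of 28 days after the last dose (Section 9.7.1.8.2)
- Non-serious collection to the last visit of the undefined Treatment Phase, taken here as Week 52 (Section 9.5.1.5.1)
- AE monitoring row of Table 2: 14 marks for 14 columns, so EOS is marked

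**Length of the gap**
- Nominal: (56 − 52) × 7 = 28 days, which equals the TEAE tail for a subject whose last dose is at Week 52.
- Shortest, with EOT late and EOS early: (392 − 7) − (364 + 7) = 385 − 371 = 14 days.
- Longest, with EOT early and EOS late: (392 + 7) − (364 − 7) = 399 − 357 = 42 days.

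**Coverage of the 28-day tail for non-serious events, last dose at the EOT visit**
- Section 9.5.1.5.1 read literally: 0 of 28 days.
- Table 2: 28 of 28 days nominally, or as few as 14 at the extremes of the visit windows.

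**Share of the TEAE window at risk under the literal reading**
- TEAE window = 364 + 28 = 392 days, and 28 / 392 = 7.1%.

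**Who is affected.** If the last dose comes *d* days before the last Treatment Period visit, the uncollected part of the tail is 28 − *d* days, and zero once *d* reaches 28. The literal reading therefore touches subjects whose last dose falls after Week 48 (52 − 4). A subject who stops earlier and stays in the study continues all assessments (Section 9.5.5), and the tail falls inside the collection period.

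**SAE windows.** SAEs are AEs, so Section 9.5.1.5.1 already covers them to Week 52, and its 28-day sentence adds to that. Section 9.5.4.1 runs through the last visit and for 28 days after the last dose. For a subject who stopped drug early and stays on study, both reach at least Week 52. They differ only in whether the weeks between EOT and EOS are included, so this is a secondary wording difference.

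**The case against.** The strongest reply is that the protocol, taken as a whole, does plan to capture these events, and much of that stands.

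- Table 2 schedules AE monitoring at Week 56.
- Section 9.5.1.5.1 itself says AEs observed during the study go on the CRF, and the study ends at EOS.
- The same section requires active enquiry at each visit about listed events since the previous one, and says such events are to be recorded.
- The undefined term may be a slip for the Randomization Phase, which the synopsis puts at approximately 56 weeks. On that reading the passages essentially agree.

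Several stronger readings might therefore be inferred but are not supported:

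- **That completers' last four weeks are unobserved.** Table 2 schedules a visit with AE monitoring at Week 56.
- **That mood and cognitive events in the tail would go unrecorded.** Psychiatric disorders and impairments of attention and memory are on the active-enquiry list. The investigator must also review PHQ-9, C-SSRS and Leiter-3 results for AEs, and all three are scheduled at EOS.
- **That the SAE sections seriously conflict.** SAEs already fall within the all-AE rule.
- **That a known fraction of subjects is affected, or that the arms would differ.** The 40% planning dropout rate is not a rate of stopping drug, since the protocol separates stopping drug from leaving the study. Nothing in the document shows a difference by arm.

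The reply does not remove the contradiction. The sentence that sets the dates uses a term the protocol does not define. The sentence extending SAEs alone by 28 days would be largely redundant for completers if all AEs were already collected to Week 56, so a site has good reason to read the cut-off as Week 52.

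**Conclusion.** The point holds as an internal contradiction about when non-serious AE collection ends. Section 9.5.1.5.1, on its most natural reading, stops at Week 52, while Table 2 and Section 9.7.1.8.2 carry on for about 28 days. At sites that follow Section 9.5.1.5.1 literally, up to 28 days (7.1%) of the TEAE window could go uncollected for a subject dosed to Week 52. At sites that follow Table 2, little or nothing would be lost.

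This rests on two assumptions: that the undefined Treatment Phase means the Treatment Period, and that the last dose is taken at about Week 52. How many sites would read the rule that way cannot be known from the document. The wording should be corrected, but it does not undermine the safety evaluation as a whole.

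**What to change.** In Section 9.5.1.5.1, replace the phrase that ends AE collection with: *through the EOS visit (Week 56) or 28 days after the last dose, whichever is later*. Use the same wording for SAEs in Sections 9.5.1.5.1 and 9.5.4.1, so that both agree with Table 2 and with the TEAE definition. This also removes the undefined phase name.

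The cost is a short amendment to two sections. The Week 56 visit and its AE monitoring already exist, so no visit is added. Where EOS falls fewer than 28 days after the last dose, or a subject leaves the study early, non-serious events would need to be asked about at the contact already required to collect SAEs for 28 days.

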9.5.1.5.2 SERIOUS ADVERSE EVENTS AND EVENTS ASSOCIATED WITH SPECIAL SITUATIONS

An SAE is any untoward medical occurrence that at any dose:

- Results in death
- Is life-threatening (ie, the subject was at immediate risk of death from the AE as it occurred; this does not include an event that, had it occurred in a more severe form or was allowed to continue, might have caused death)
- Requires inpatient hospitalization or prolongation of existing hospitalization
- Results in persistent or significant disability/incapacity
- Is a congenital anomaly/birth defect (in the child of a subject who was exposed to the study drug)

Other important medical events that may not be immediately life-threatening or result in death or hospitalization but, when based on appropriate medical judgment, may jeopardize the subject or may require intervention to prevent one of the outcomes in the definition of SAE listed above should also be considered SAEs. Medical and scientific judgment should be exercised in deciding whether expedited reporting is appropriate in such situations.

For this study, the following events should always be considered serious and reported as an important medical event if it does not meet other serious criteria:

- Serotonin syndrome (must have at least 1 of the following: Spontaneous clonus; Inducible clonus plus agitation or diaphoresis; Ocular clonus plus agitation or diaphoresis; Tremor plus hyperreflexia; Hypertonia plus temperature above 38°C plus ocular clonus or inducible clonus)
- Psychosis
- Suicidal behavior
- Priapism
- New onset valvular heart disease
- New onset pulmonary hypertension
- Malignant neoplasms (revised per Amendment 03)
- Fibroadenomas of the breast or ductal carcinoma in situ
- Severe symptomatic hypoglycemia (revised per Amendment 03)

In addition to the above, events associated with special situations include pregnancy or exposure to study drug through breastfeeding; AEs associated with study drug overdose, misuse, abuse, or medication error. These events associated with special situations are to be captured using the SAE procedures but are to be considered as SAEs only if they meet 1 of the above criteria. All AEs associated with special situations are to be reported on the CRF whether or not they meet the criteria for SAEs.

All SAEs must be followed to resolution or, if resolution is unlikely, to stabilization.

The following hospitalizations are not considered to be SAEs because there is no “AE” (ie, there is no untoward medical occurrence) associated with the hospitalization:

- Hospitalizations for respite care
- Planned hospitalizations required by the protocol
- Hospitalization planned before informed consent (where the condition requiring the hospitalization has not changed after study drug administration)
- Hospitalization for administration of study drug or insertion of access for administration of study drug
- Hospitalization for routine maintenance of a device (eg, battery replacement) that was in place before study entry

9.5.1.5.3 LABORATORY MEASUREMENTS

Clinical laboratory tests to be performed, including hematology, chemistry, and urinalysis, are summarized in [Table 1](#). Subjects should be in a seated or supine position during blood collection. The Schedule of Procedures/Assessments ([Table 2](#)) shows the visits and time points at which blood for clinical laboratory tests and urine for urinalysis will be collected in

the study. Laboratory testing should be conducted on an unscheduled basis if clinically indicated. (revised per Amendment 03)

Table 1 Clinical Laboratory Tests (revised per Amendments 01, 03, and 04)

Category	Parameters
Hematology	Hematocrit, hemoglobin, platelets, RBC count, and WBC count with differential (bands, basophils, eosinophils, lymphocytes, monocytes, neutrophils)
Chemistry	
Electrolytes	Chloride, potassium, sodium, bicarbonate
Liver function tests	Alanine aminotransferase, alkaline phosphatase, aspartate aminotransferase, gamma glutamyl transpeptidase, direct bilirubin, total bilirubin
Renal function tests	Blood urea/blood urea nitrogen, creatinine
Thyroid function	T4, TSH
Adrenal function	AM serum Cortisol
Sex hormones	Testosterone (male subjects), estradiol (female subjects)
Bone health assessments	Serum OC and PICP, Hydroxy-proline; Urine NTX
Prolactin	Fasting prolactin levels
Other (revised per Amendments 01 and 04)	Albumin, calcium, globulin, fasting plasma glucose, HbA _{1c} , HDL cholesterol, fasting insulin, lactate dehydrogenase, LDL cholesterol, fasting lipid panel, phosphorus, total protein, total cholesterol, triglycerides, uric acid, urine β-hCG
Urinalysis	Bacteria, casts, crystals, epithelial cells, glucose, ketones, occult blood, pH, protein, RBCs, specific gravity, WBCs

β-hCG = beta-human chorionic gonadotropin, HbA_{1c} = hemoglobin A_{1c}, HDL = high density lipoprotein, LDL = low density lipoprotein, OC = osteocalcin; NTX = N-telopeptide, PICP = carboxyterminal propeptide of type I procollagen; RBC = red blood cell, T4 = thyroxine, TSH = thyroid stimulating hormone, WBC = white blood cell.

Clinical laboratory tests during the study will be performed by a central laboratory. All blood and urine samples will be collected and sent to the central laboratory on the day of collection unless otherwise instructed. In cases of a safety concern, blood samples will be split (or 2 samples drawn) to allow a local laboratory analysis in addition to the central laboratory.

A laboratory abnormality may meet the criteria to qualify as an AE as described in this protocol (see [Section 9.5.1.5.1](#)) and the CRF Completion Guidelines. In these instances, the AE corresponding to the laboratory abnormality will be recorded on the Adverse Event CRF.

9.5.1.5.4 VITAL SIGNS AND WEIGHT MEASUREMENTS

Vital sign measurements (ie, systolic and diastolic BP [mmHg], pulse [beats per minute], respiratory rate [per minute], body temperature [in centigrade]), and weight (kg) will be obtained as designated in the Schedule of Procedures/Assessments (Table 2) by a validated method. BP and pulse will be measured after the subject has been sitting for 5 minutes. All BP measurements should be performed on the same arm, preferably by the same person.

When vital signs are to be obtained concurrently with PK or other blood samples, the vital sign measurements will be performed before drawing blood samples in order to maximize the accuracy of blood sampling times while minimizing the potential effects of blood drawing on recordings obtained during safety assessments.

9.5.1.5.5 HEIGHT MEASUREMENTS

Height (cm) measurements will be obtained in triplicate to the nearest 0.1 cm as designated in the Schedule of Procedures/Assessments (Table 2). (revised per Amendment 03)

9.5.1.5.6 CDC GROWTH MEASUREMENTS

Investigators will calculate the height for age percentile and weight for age percentile utilizing the most recent CDC 95th Percentile Growth Chart and the height and weight measurements obtained, as designated in the Schedule of Procedures/Assessments (Table 2). (revised per Amendment 01)

9.5.1.5.7 WAIST CIRCUMFERENCE

Waist circumference (cm) measurements will be obtained in triplicate to the nearest 1.0 cm taken 3 times at each visit as designated in the Schedule of Procedures/Assessments (Table 2). (revised per Amendments 01 and 03)

9.5.1.5.8 PHYSICAL EXAMINATIONS

Physical examinations will be performed as designated in the Schedule of Procedures/Assessments (Table 2). Documentation of the physical examination will be included in the source documentation at the site. Significant findings at the Screening Visit will be recorded on the Medical History and Current Medical Conditions CRF. Changes from screening physical examination findings that meet the definition of an AE will be recorded on the Adverse Events eCRF.

As part of the physical examination, a neuromuscular sign assessment for serotonin syndrome will be performed for potential serotonergic syndrome components. Serotonergic syndromes that meet the diagnostic criteria will be captured by AE eCRF. (revised per Amendment 01)

Signs and symptoms of priapism (painful erection) and hyperprolactinemia (menstrual cycle abnormalities or galactorrhea) will also be captured in the AE eCRF. (revised per Amendment 01)

